B. To evaluate the efficacy of uninterrupted transdermal NTG therapy in improving other symptom- and quality-of-life outcomes associated with hot flashes in peri- and postmenopausal women.

We hypothesize that, compared to placebo, uninterrupted use of NTG will result in significant improvements in sleep quality, anxiety and depression symptoms, and menopause-related quality of life over 12 weeks.

C. To examine the tolerability and safety of uninterrupted transdermal NTG therapy in peri- and postmenopausal women with hot flashes.

We hypothesize that, compared to placebo, uninterrupted use of NTG will be associated with higher rates of mild headache, but no significant differences in rates of chest pain, syncope, or severe adverse events defined by Common Terminology for Adverse Event Criteria severity grade 3 or higher.

C. BACKGROUND & RATIONALE

C.1 Background

Hot flashes (a.k.a. vasomotor symptoms) are the most common symptomatic complaint of menopausal women in the United States, with over two thirds reporting hot flashes at some point during the menopausal transition, and one in five reporting symptoms severe enough to require treatment (Gold, Sternfeld et al. 2000, Huang, Grady et al. 2008, Avis, Crawford et al. 2015). Although estrogen therapy is effective in suppressing hot flashes, it is associated with an increased risk of endometrial cancer, and when combined with a progestin to prevent endometrial hyperplasia, its long-term use can increase risk of coronary disease, thromboembolic events, and breast cancer (Rossouw, Anderson et al. 2002, Shumaker, Legault et al. 2003, Manson, Chlebowski et al. 2013).

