In the event that a participant develops a potentially severe adverse event such as chest pain during weaning, she will be directed to seek immediate emergency attention, just as she would during any other time point of the study. Although all study medication will be stopped while the participant receives emergency care, it should be possible to manage any side effects safely in the emergency care setting regardless of medication discontinuation.

Study coordinators will also try to schedule and complete a post-discontinuation telephone call that will occur at least 28 days after discontinuation of study medication, to promote appropriate monitoring of adverse events following discontinuation of study drug.

K. STATISTICAL CONSIDERATIONS

K.1 General Design Issues

A randomized, parallel-group, placebo-controlled trial design has been selected to examine the following aims and test the following hypotheses related to the efficacy, safety, and tolerability of transdermal NTG for treatment of menopausal hot flashes:

Objective 1: Determine the efficacy of uninterrupted transdermal NTG therapy in reducing the frequency of hot flashes in peri- and postmenopausal women.

Hypothesis 1: Compared to placebo, uninterrupted use of NTG will result in at least a 20% greater decrease in the frequency of hot flashes (measured by validated symptom diaries) over 12 weeks.

Objective 2: To evaluate the efficacy of uninterrupted transdermal NTG therapy in reducing the severity of hot flashes in peri- and postmenopausal women.

Hypothesis 2: Compared to placebo, uninterrupted use of NTG will result in significant improvements in frequency of moderate-to-severe hot flashes and in cumulative hot flash severity score (assessed by validated symptom diaries) over 12 weeks.

Objective 3: Evaluate the efficacy of uninterrupted transdermal NTG therapy in improving other symptom- and quality-of-life outcome associated with hot flashes in peri- and postmenopausal women.

Hypothesis 3: Compared to placebo, uninterrupted use of NTG will result in significant improvements in hot flash-related sleep quality, anxiety and depression, and menopause-related quality of life over 12 weeks.

Objective 4: Examine the tolerability and safety of uninterrupted transdermal NTG therapy in peri- and postmenopausal women with hot flashes.

Hypothesis 4: Compared to placebo, uninterrupted use of NTG will be associated with higher rates of mild

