headache during the first 24 hours of therapy, but no significant differences in rates of chest pain, syncope, or severe adverse events defined by CTCAE severity grade 3 or higher.

K.2 Data Analyses

K.2.1 Analyses for Objective 1

Analyses to address aim 1 will examine change in average daily hot flash frequency from baseline to 4 and 12 weeks of treatment, measured over 7 days by validated hot flash diaries (Sloan, Loprinzi et al. 2001, Food and Drug Administration 2003). The effect of NTG therapy will be estimated using linear mixed models (LMMs) for the repeated changes, adjusting for baseline values, under the assumption of an approximately constant treatment effects at 4 and 12 weeks; in supplementary analysis we will assess evidence for differences in the treatment effects at these two time points. The distribution of the LMM residuals will be assessed using Q-Q plots, and outcomes will be transformed if necessary to achieve approximate normality. Analyses will be by intention to treat, according to treatment assignment, and without regard to adherence.

K.2.2 Analyses for Objective 2

For additional confirmation of treatment effects on frequency of any hot flashes, we will also assess treatment effects on moderate-to-severe hot flashes and on total hot flash severity scores as secondary outcomes, also assessed by diary, using the same methods. The distribution of the LMM residuals will again be assessed using Q-Q plots, and outcomes will be transformed if necessary to achieve approximate normality. Analyses will again be by intention to treat, according to treatment assignment, and without regard to adherence.

K.2.3 Analyses for Objective 3

Analyses to address aim 2 will examine changes in sleep quality and duration, anxiety and depressive symptoms, and menopausal quality-of-life from baseline to 4 and 12 weeks. These outcomes will be captured by scores on validated self-administered questionnaires, with supplementation by sleep diary in the case of sleep duration. Intervention effects on these outcomes will be estimated using LMMs, adjusted for baseline scores. Approximate normality of the residuals will be checked using Q-Q plots, and outcomes will be transformed if necessary. Analyses will once again be by intention to treat and without regard to adherence.

K.2.4 Analyses for Objective 4

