To assess tolerability and safety of NTG, we will compare group-specific rates of: 1) severe symptoms that are potentially attributable to NTG therapy (i.e., headache limiting activities of daily living, chest pain or tightness limiting activities of daily living, or syncope/fainting); and 2) any adverse events with a severity rating of 3 or higher on the CTCAE severity scale (National Cancer Institute 2009). We will also examine group-specific rates of all adverse events, regardless of severity and of anticipated relationship to NTG therapy. Inferences for rare outcomes will be obtained using Fisher's exact test. Because intention-to-treat analysis is conservative, any suggestive differences in safety outcome rates will be assessed accounting for adherence, final dose, and their interactions with treatment.

K.3 Sample Size Determination

Sample size calculations are based on parameter estimates from prior pharmacologic hot flash trials conducted by the investigators such as the FAST(Grady, Cohen et al. 2007) and CHIMES trials (Grady, Sawaya et al. 2009), which had similar eligibility criteria with respect to age, hot flashes, and treatment history. We assume the study sample will be characterized by: a) mean baseline hot flash frequency of >9 hot flashes/day; b) mean reduction in hot flash frequency in the control group of <3 hot flashes/day (i.e., <33%); c) standard deviation of change in hot flash frequency of ~4.5 hot flashes per day; and d) correlation between baseline and follow-up values of ~0.55.

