Under these assumptions, a sample size of 140 (70 per group) should provide an estimated 87% power in 2-sided tests with type-I error of 5% to detect an 20% greater reduction in hot flash frequency (or 1.8 hot flashes per day) in the active treatment arm relative to the control arm. This will correspond to a 50-55% decrease in hot flash frequency from baseline in the active treatment group, which has previously been described as a clinically important effect in prior hot flash research (Butt, Deng et al. 2007). Estimates account for correlation of the repeated measures and loss to follow-up of up to 15%, and indicate that power will remain $\geq 80\%$ even if actual effect size or other parameters are less favorable than expected. This sample of 70 per group will also provide $>80\%$ power in 2-sided tests with type-I error of 5% to detect a between-group difference in mean frequency of moderate-to-severe hot flashes of ~ 1.5 hot flashes per day, as well as ~ 3.3 points in hot flash severity scores.

K.4 Additional Statistical Considerations

K.4.1 Drop-out rates

Based on past experience, participant dropout levels are expected to remain under 15% over 12 weeks. The assumption of non-informative dropout will be examined by comparing the baseline characteristics and early post-randomization outcomes of participants who are lost to follow-up versus retained in the study. If drop-out rates differ substantially between groups, analyses will be adjusted for baseline covariates associated with retention. In sensitivity analyses, we will also use multiple imputation of missing outcomes under plausible informative missingness assumptions, along with standard methods for calculating summary estimates and confidence intervals, to assess the potential impact of loss to follow-up on treatment effect estimates (Schafer 1999).

K.4.2 Dose effects

In the event that an overall treatment benefit is detected over 12 weeks, we will conduct exploratory analyses to probe for differences in the magnitude of treatment effects by highest-achieved NTG dose, by testing for interaction between treatment assignment and highest-achieved NTG dose in a linear mixed model for change in hot flash frequency. This analysis will control for the main effect of highest achieved dose to control the placebo effect of this self-selected variable, as well as baseline factors that may confound it, such as age, body mass index, and baseline hot flash frequency or severity.

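### The safety hypothesis predicts non-significance for chest pain, syncope and grade 3+ events, and the plan specifies no interval on the between-arm difference, so at 70 per arm an uninformative result would agree with it

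*Combined protocol and SAP*

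**What the plan says.** Section K.1 says the design was chosen to "test the following hypotheses related to the efficacy, safety, and tolerability of transdermal NTG", so safety is among the tested hypotheses. Its Hypothesis 4 predicts "no significant differences in rates of chest pain, syncope, or severe adverse events defined by CTCAE severity grade 3 or higher". Section B.2, objective C, carries the same prediction: "higher rates of mild headache, but no significant differences in rates of chest pain, syncope, or severe adverse events".

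Section K.2.4 sets the analysis. It states that "we will compare group-specific rates of" severe symptoms potentially attributable to nitroglycerin and adverse events of CTCAE grade 3 or higher. It adds: "Inferences for rare outcomes will be obtained using" Fisher's exact test. It then provides that "any suggestive differences in safety outcome rates will be assessed accounting for adherence, final dose, and their interactions with treatment". No risk difference, interval or margin is named.

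Confidence intervals appear once in section K, in K.4.1, where multiple imputation of missing outcomes will use "standard methods for calculating summary estimates and confidence intervals". Section K.3 states that "a sample size of 140 (70 per group) should provide an estimated 87% power", but that figure is for hot flash frequency. The other power statements there also concern diary outcomes, and none concerns safety.

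**The concern.** A hypothesis of no significant difference is met by any non-significant result. With few events, non-significance is likely whether or not risk is raised, unless the rise is large. A report that follows the stated hypothesis and the one named test could therefore present an uninformative comparison as agreeing with the safety hypothesis.

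Safety is a stated objective, and section I.1.1 discusses a theoretical risk of chest pain or coronary events under continuous nitrate in people with existing coronary disease. Readers will want to know how large an excess the trial leaves open. The specified p-value does not tell them.

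**Working it through.** **Inputs.** 70 women per arm and a two-sided 5% level, both from K.3 (K.2.4 gives no level). The documents state no expected rate for chest pain, syncope or grade 3+ events. I.1.1 describes hypotension severe enough to cause syncope as uncommon, and the 19-woman pilot reported no chest pain. All event rates below are therefore assumptions, and the count pairs are illustrations.

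**The plan's own figure.** There is no safety power to reproduce. The 87% in K.3 concerns efficacy. It comes out close if all visits are assumed to correlate at 0.55 and 70 × 0.85 = 59.5 per arm remain:
- raw SD = 4.5/√(2 × 0.45) = 4.743;
- baseline-adjusted SD of the mean of two diaries = 4.743 × √(1.55/2 − 0.55²) = 3.261;
- power = Φ(1.8/(3.261 × √(2/59.5)) − 1.96) = 85.3%.

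The safety point does not depend on this.

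**Step 1: events needed for Fisher p<0.05.** With x events on nitroglycerin and none on placebo, the two-sided p is 2 × C(70,x)/C(140,x). This gives 0.058 at x = 5 and 0.028 at x = 6. The smallest significant splits are:
- 6 v 0, p = 0.028;
- 8 v 1, p = 0.033;
- 10 v 2, p = 0.031.

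**Step 2: exact Fisher power.** Power is the sum, over all 71 × 71 tables with p<0.05, of Bin(a; 70, p₁) × Bin(b; 70, p₀).

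| Assumed true rates, nitroglycerin v placebo | 70 per arm | 60 per arm (about 15% lost) |
|---|---|---|
| 3% v 1% | 1.0% | 0.5% |
| 5% v 1% | 7.6% | 4.6% |
| 8% v 1% | 31.9% | 22.7% |

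At 5% v 1% the result would be non-significant in 100 − 7.6 = 92.4% of trials. With a 1% placebo rate, 80% power at 70 per arm needs a nitroglycerin rate of about 13.8%.

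**Step 3: what a non-significant table leaves open.** With arm proportions p₁, p₂ and Wilson limits (l, u), d = p₁ − p₂ and the Newcombe limits are
- lower: d − √((p₁ − l₁)² + (u₂ − p₂)²);
- upper: d + √((u₁ − p₁)² + (p₂ − l₂)²).

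For 4 v 1, in percentage points: p₁ = 5.71 (Wilson 2.24 to 13.79), p₂ = 1.43 (0.25 to 7.66), d = 4.29. The upper limit is 4.29 + √(8.08² + 1.18²) = 12.4 and the lower is 4.29 − √(3.47² + 6.23²) = −2.8.

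| Events | Fisher p | Newcombe 95% interval (points) |
|---|---|---|
| 0 v 0 | 1.00 | −5.2 to +5.2 |
| 1 v 0 | 1.00 | −3.9 to +7.7 |
| 2 v 1 | 1.00 | −5.1 to +8.5 |
| 3 v 1 | 0.62 | −4.0 to +10.5 |
| 4 v 1 | 0.37 | −2.8 to +12.4 |

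With 60 per arm the upper limit at 0 v 0 is 6.0.

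**Step 4: the two methods can disagree.** At 5 v 0, Fisher p = 0.058 while Newcombe gives +0.5 to +15.7. The same happens at 7 v 1 (p = 0.063) and 9 v 2 (p = 0.055), where the Newcombe interval also lies above zero. The role of each must therefore be fixed before the data are seen.

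**The case against.** The strongest reply is that this argues from silence. Section K is terse throughout: K.2.1 names no confidence interval for the primary outcome either, and nobody would conclude that none will be given. K.2.4 does not exclude an interval, and arm-specific rates with arm sizes would let a reader compute one. That stands. The accurate statement is that no interval is specified, not that none will be produced.

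Second, a reader might infer that the plan will declare the drug safe when p exceeds 0.05. The documents do not say so. No passage makes non-significance a pass rule, Objective 4 is worded as an examination, and K.2.4 follows up suggestive differences without requiring significance. What remains is narrower: the listed hypothesis is one with which non-significance agrees. The follow-up does not fill the gap. It is triggered only by a suggestive difference and brings in adherence and final dose, both arising after randomisation, so it adds no interval on the randomised comparison. Review of unblinded data by the monitoring board (I.4) protects participants during the trial but does not govern how the final comparison is worded.

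Third, low power for rare harms is usual in a trial of 140 women sized on efficacy and is not itself a defect. That also stands, and no larger sample is asked for. Nor is non-significance empty: it argues against very large excesses. Only an interval says how large.

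Fourth, a reader might extend the low-count premise to all three outcomes. The documents support it for syncope and chest pain only. Severe headache lies outside the no-difference clause, and the plan does not call it rare.

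**Conclusion.** The point holds as a cheap improvement to wording and reporting. A tested hypothesis of no significant difference, paired with Fisher's test as the only specified inference for rare outcomes, lets an uninformative result agree with the safety hypothesis. Under an assumed fivefold rise from 1% to 5%, that would happen about 92% of the time at 70 per arm. If counts are low, the data would still leave room for an excess of about 5 to 12 points. That range rests on the chosen pairs from 0 v 0 to 4 v 1 and on the Newcombe method. For grade 3+ events it is conditional, because the documents do not indicate how many to expect.

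The disagreement between methods does not show that the interval should override the prespecified Fisher test. That would be a preference, and the defect does not require it. Efficacy conclusions are unaffected.

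**What to change.** - In K.1 and B.2, reword the chest pain, syncope and grade 3+ part of Hypothesis 4 as estimation of the between-arm difference.
- In K.2.4, beside the arm-specific rates and the Fisher test, add a risk difference by randomised arm with a prespecified 95% interval (for example Newcombe) for chest pain, syncope and grade 3+ events. An interval for severe headache is optional.
- Report the upper limit in words, so that the reader sees the excess above which the interval rules values out.
- State that p>0.05 will not be described as evidence of similar risk.
- State in advance that Fisher remains the test and the interval is the estimate, and that both are reported when they disagree.

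The cost is a few sentences in three sections and one column in the safety table. No new data are needed, and sample size and primary analysis do not change. The downside is that the intervals will be wide and the safety conclusion more cautious.

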Following run-in, eligible women will be randomized in equal ratios to the NTG or placebo interventions using a computer algorithm with randomly permuted blocks of size 2 and 4. To ensure similar distribution of women of different menopausal stages in each group, randomization will be stratified by menopausal stage (i.e., postmenopausal vs late menopausal transition), although there will be no pre-set sample size threshold for any specific stratum. Within each category, randomization numbers identifying the supply of medication for each participant will be generated and then assigned sequentially in the order participants are randomized.

To avoid manipulation of randomization, standard allocation concealment procedures will be followed (Schulz and Grimes 2002). Randomization numbers will be pre-printed on medication foil packets and master packs, prepared by Clinical Trials Services. At baseline, after screening data have been reviewed and the principal investigator has confirmed eligibility, a coordinator will enter the date and participant ID into the randomization log next to the number that has not yet been assigned, and dispense a supply of the drug identified by the randomization number. To provide a check on validity, an analyst will check that the randomization dates and times follow the order of the sequence numbers.

Based upon randomization, participants will be given a supply of either 0.2 mg/hr NTG or placebo patches and will be instructed to apply their first patch that night and change their patches on a nightly basis, without any patch-free periods, until the 1-week visit.

C. Blinding

Consistent with a double-blinded design, participants, investigators, and any study staff who have contact with participants or role in assessing outcomes will be blinded to treatment assignment. Only the statistician responsible for generating the randomization scheme and the staff of Clinical Trials Services contracted to package the active and placebo patches will have access to treatment assignment. Unless stipulated by the Data & Safety Monitoring Board or required for management of a participant with a serious adverse event, assignment codes will not be broken until all participants have completed the study, the trial data are cleaned, and the dataset is locked.

H.2.5 Follow-up visits

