K.4.5 Subgroup analyses

After assessing overall treatment effects, we will explore differences in treatment effects within select subgroups defined by key demographic and clinicopathologic factors in multivariate regression analysis. For example, we will explore whether age, menopausal stage, body mass index, and use of estrogen receptor modulators influence treatment effects on primary and secondary outcomes. Analyses will necessarily be exploratory, as the study will be primarily powered to detect overall treatment effects rather than subgroup effects. Subgroup estimates will be considered only if the interaction between treatment and subgroup is significant at $p < 0.05$.

L. DATA COLLECTION AND QUALITY ASSURANCE

L.1 Data Collection Forms

Study data will be obtained from participant-completed symptom diaries and medication diaries, participant- or interviewer-administered questionnaires, physical examination measures, and blood and urine sampling/testing. Forms for recording or abstracting data will be developed specifically for this study, including:

- Hot flash diary abstraction form: After participants complete their diary at home, they will return the completed diary to the study clinic, and diary data will be abstracted by trained study coordinators using

a paper-based Hot Flash Diary Abstraction Form. Data from abstraction forms will then be entered into the electronic database by a blinded staff member.

- Questionnaires assessing sleep quality, menopause-related quality of life, mood, and participant satisfaction. Participants will complete these self-report questionnaires during clinic- or video-based study visits. In most cases, participants will enter directly into an electronic tablet or laptop computer or use an electronic questionnaire link; however, if a participant prefers to record her responses on a paper-based questionnaire form, a blinded staff member will then enter the data into the electronic database after the visit.
- Questionnaires assessing demographic history, general medical history, medication use, and tobacco and alcohol use: These questionnaires will be administered by a clinical coordinator during telephone and clinic- or video-based study visits; data from questionnaires will be directly entered by the coordinator into the electronic database.

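### Minor: randomisation is stratified by menopausal stage, but the efficacy models leave stage out, so the reported standard error may be slightly too wide

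*Combined protocol and SAP*

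**What the plan says.** Under H.1.4 B, "randomization will be stratified by menopausal stage (i.e., postmenopausal vs late menopausal transition", with blocks of 2 and 4 and no target size for either stratum.

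The efficacy models are in K.2. For the primary outcome, K.2.1 states: "The effect of NTG therapy will be estimated using linear mixed models (LMMs) for the repeated changes, adjusting for baseline values". K.2.2 applies the same method to moderate-to-severe hot flashes and the severity score. For sleep, mood and quality of life, K.2.3 states: "Intervention effects on these outcomes will be estimated using LMMs, adjusted for baseline scores". Menopausal stage appears in none of them.

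Four other clauses bear on covariates:

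- **G.1.4** collects baseline characteristics partly so that adjustments can be made if the arms turn out to differ significantly.
- **K.4.1**: "If drop-out rates differ substantially between groups, analyses will be adjusted for baseline covariates associated with retention".
- **K.4.2**, the exploratory dose analysis, controls for "baseline factors that may confound it, such as age, body mass index, and baseline hot flash frequency or severity". Stage is not named, though the list is open.
- **K.4.5** names stage, but only as an exploratory effect modifier: "we will explore whether age, menopausal stage, body mass index, and use of estrogen receptor modulators influence treatment effects on primary and secondary outcomes".

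**The concern.** Stratified blocks force the two arms to have nearly the same mix of stages. If stage predicts change in hot flash frequency once the baseline value is accounted for, the design removes that source of variation from the comparison of arms. A model that omits stage does not know this. It counts the between-stage variation as residual noise, so its standard error overstates the true variability of the estimate. The interval is wider than it need be and the test rejects less often than 5% under the null.

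The other clauses do not repair this. The G.1.4 trigger in practice cannot select stage, because the blocks keep stage balanced. K.4.1 could bring stage in only if drop-out differs between arms and stage is associated with retention. K.4.2 and K.4.5 are exploratory.

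At stake is some precision that the design has already paid for. Validity is not at stake.

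**Working it through.** **Inputs from K.3.** "standard deviation of change in hot flash frequency of ~4.5 hot flashes per day"; correlation of about 0.55 between baseline and follow-up; difference sought 1.8/day; 140 women; up to 15% loss, so 140 × 0.85 = 119 analysed; two-sided 5%.

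**Assumptions not in the documents.** Correlation of 0.55 between the two follow-up diaries; share in late transition p = 0.30 (varied below); stage effect d on change, given baseline, of 0, 1, 2 or 3 per day.

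**Reproducing the plan's power.** K.2.1 assumes a roughly constant effect at both time points, so the relevant quantity is the mean of two follow-ups adjusted for baseline.

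- Variance of a single value: 4.5² / (2 × (1 − 0.55)) = 22.5 (SD 4.74).
- Residual variance: 22.5 × ((1 + 0.55)/2 − 0.55²) = 10.63 (SD 3.26).
- Standard error of the difference: 2 × 3.26/√119 = 0.598.
- Power for 1.8/day: 85.3% by the normal approximation, 84.8% by the noncentral t.

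This is within about 2 points of the stated 87%. A correlation of 0.50 between follow-ups gives about 87%, and reading 4.5 as the SD of the values instead of the changes gives 88.8%. The gap from 87% reflects these readings and has nothing to do with omitting stage.

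**Effect of omitting stage.** Between-stage variance is p(1 − p)d². With stage in the model, SE = 2 × √(10.63 − p(1 − p)d²)/√119. Without it, the model reports 0.598, although balanced blocks give the estimate the smaller true SE. Power without stage therefore uses the smaller true SE but tests against 0.598.

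| Stage effect (/day) | SE with stage | Reported SE too wide by | 95% CI half-width, without → with stage | Power without stage | Power with stage |
|---|---|---|---|---|---|
| 0 | 0.598 | 0% | 1.18 → 1.18 | 84.8% | 84.8% |
| 1 | 0.592 | 1% | 1.18 → 1.17 | 85.0% | 85.5% |
| 2 | 0.574 | 4% | 1.18 → 1.14 | 85.7% | 87.5% |
| 3 | 0.542 | 10% | 1.18 → 1.07 | 87.1% | 90.9% |

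For example, at d = 2: 0.30 × 0.70 × 4 = 0.84; 10.63 − 0.84 = 9.79; 2 × √9.79/√119 = 0.574; 0.598/0.574 = 1.04.

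In power terms the gain equals about 0, 2, 6 and 15 more women analysed. For shares from 15% to 50%, the power gain is 0.3 to 0.5 points at 1/day, 1.1 to 2.1 at 2/day and 2.4 to 4.4 at 3/day.

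**Simulation checks.** With 140 women randomised in blocks of 2 and 4 within stage, 119 retained at random, p = 0.30 and 20,000 trials per setting, power without and with stage was 84.2% and 84.5% at 1/day, 85.2% and 87.1% at 2/day, and 86.6% and 90.7% at 3/day. Type I error without stage fell to 4.6% at 2/day and 3.3% at 3/day. With stage it was 4.8% to 5.4%. A separate simulation (8,000 trials per setting, smaller-stratum shares of 20% and 50%) gave 4.3% to 4.4% without stage at 2/day and 4.9% to 5.0% with it, so the values slightly above 5% in the first run look like chance.

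**Can the G.1.4 trigger pick up stage?** At randomisation the blocks cap the difference between arms at 2 women in the late-transition stratum. In 10,000 simulated randomisations at each share of 15%, 30% and 50%, the smallest chi-square p-value for stage was 0.54.

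**The case against.** The omission itself is not in dispute; its importance is. At 1/day the interval half-width moves by about 0.01 and power by about half a point. The size depends on two quantities that the documents do not give. With only 10% of women in late transition, the excess in the standard error at 1/day is 0.4%; at 0.5/day it is 0.3% or less for any split. Only the stage effect left after adjusting for baseline frequency counts, and no section says that any remains: H.1.4 B justifies stratification by balance, not by prognosis. A stage effect of 3/day would be as large as the upper limit K.3 sets for the control group's mean reduction. The figures also cover only the primary outcome, since no SD is given for the K.2.3 scores.

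All of this stands, and it limits the point to a minor one. It does not give a reason to leave stage out: if stage is irrelevant, including it costs under 0.1% of the standard error.

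It is also fair that ruling out covariates prompted by observed baseline differences is a separate matter from the stage term. The two can be decided independently.

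**Conclusion.** The concern holds and is minor. Stage is used to randomise and is not a planned covariate in any efficacy model. The error is in the conservative direction: an interval and a test that may understate the precision of the design. On the primary outcome, with K.3's inputs, a correlation of 0.55 between follow-ups and 30% in late transition, the reported standard error is about 1% too wide if stage shifts change by 1/day. It is not too wide at all if stage has no effect. The 4% and 10% figures need effects of 2 and 3 per day, larger than the treatment effect sought. Extending the recommendation to the secondary outcomes rests on the same logic but is not quantified.

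**What to change.** In K.2.1 to K.2.3 write: *Every efficacy LMM will include, as fixed effects, treatment, visit, the baseline value of the outcome, and menopausal stage as randomised.* The stage term is what this point requires; listing visit simply makes the specification complete.

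A useful companion sentence for K.2.1, which can be decided separately, is: *Covariates will not be added to the primary model because of observed baseline differences between groups.* G.1.4 would then be amended to match, for example by saying that baseline characteristics are presented descriptively by group.

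Two data-dependent steps remain and are not addressed here: the drop-out adjustment in K.4.1, and the rule in K.2.1 that "outcomes will be transformed if necessary to achieve approximate normality".

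The cost is two sentences in K.2, a matching edit in G.1.4 and one degree of freedom. Stage is already recorded for randomisation, so no new data and no change in sample size are needed. The change should be made before treatment codes are broken.
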